Key Secondary Objectives If LY2951742 (120 or 240 mg/month) is statistically significantly superior to placebo on the primary objective, the following key secondary objectives will be tested with adjustment for multiplicity:	The specific methodology (including testing order, relationship and type I error allocation and propagation) for the tests of the following key secondary endpoints will be specified in Section 5.5.10.4.	
To compare LY2951742 with placebo with respect to 50% response rate	The proportion of patients with reduction from baseline ≥50% in monthly migraine headache days during the 3-month double-blind treatment phase	
To compare LY2951742 with placebo with respect to 75% response rate	The proportion of patients with reduction from baseline ≥75% in monthly migraine headache days during the 3-month double-blind treatment phase	
To compare LY2951742 with placebo with respect to 100% response rate	The proportion of patients with reduction from baseline of 100% in monthly migraine headache days during the 3-month double-blind treatment phase	
To compare LY2951742 with placebo with respect to change in functioning	The mean change from baseline in the Role Function-Restrictive domain score of the Migraine-Specific Quality of Life Questionnaire version 2.1 (MSQ v2.1) at Month 3	
To compare LY2951742 with placebo with respect to change in use of acute (abortive) migraine treatment	The overall mean change in the number of monthly migraine headache days requiring medication for the acute treatment of migraine or headache during the 3-month double-blind treatment phase	
To compare LY2951742 with placebo with respect to change in global severity of the migraine condition	Mean change from baseline in the Patient Global Impression of Severity (PGI-S) score at Month 3	

Objectives and Endpoints

2	Objectives (cont.)	Endpoints (cont.)
Other Se	econdary Objectives	
• To c	compare LY2951742 with placebo n respect to change in headache days	The overall mean change from baseline in the number of monthly headache days during the 3-month double-blind treatment phase
with	compare LY2951742 with placebo n respect to change in moderate to ere headache days	• The overall mean change from baseline in the number of monthly moderate to severe headache days during the 3-month double-blind treatment phase

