5.5.1.1. Adjustments for Covariates

The MMRM models will include the fixed, categorical effects of treatment, pooled country, month, baseline medication overuse (yes versus no), concurrent prophylaxis (yes versus no), and treatment-by-month interaction, as well as the continuous, fixed covariates of baseline value and baseline value-by-month interaction. The baseline value and baseline-by-month interaction are included to account for the differential influence over time that the baseline value has on the postbaseline values. Rules for pooling countries are defined in Section 5.5.1.3. Pooled country will be excluded in MMRM models for safety measures.

When an ANOVA model is used to analyze a continuous efficacy variable, the model will contain the main effects of treatment, baseline medication overuse (yes versus no), concurrent prophylaxis use (yes versus no) and pooled country. When an ANCOVA model is used to analyze a continuous efficacy variable, the model will contain the main effects of treatment, baseline medication overuse (yes versus no), concurrent prophylaxis use (yes versus no) and pooled country, and appropriate baseline value as a covariate. When an ANOVA or ANCOVA model is used to analyze a continuous safety variable, pooled country will be removed from the model.

The GLIMMIX models for the repeated binary outcomes will include the fixed, categorical effects of treatment, month, baseline medication overuse (yes versus no), concurrent prophylaxis (yes versus no), and treatment-by-month interaction, as well as the continuous, fixed covariate of baseline value. Pooled country and the baseline value-by-month interaction will be excluded from the model in order to increase the likelihood of convergence.

When a logistic regression is used to analyze a binary variable, the model will include the main effect of treatment, baseline medication overuse (yes versus no), concurrent prophylaxis use (yes versus no) and pooled country, and appropriate baseline value as a covariate. Pooled country may be excluded from the model in case of non-convergence.

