5.5.10.3. Secondary and Exploratory Efficacy Analyses

Key secondary efficacy measures will be tested with adjustment for multiple testing as specified in Section 5.5.10.4.

Other planned secondary and exploratory efficacy analyses will be conducted without multiplicity adjustment. Table CGAI.5.5 summarizes all the planned (unadjusted) secondary and exploratory efficacy analyses for SP III, SP III/IV, and SP III/IV/V, additional statistical analysis details are also provided below.

Continuous Secondary Efficacy Measures

For the continuous secondary efficacy measures, the change from baseline to each postbaseline period will be estimated for each treatment from repeated measures analyses as described for analysis for primary outcome.

For the continuous secondary efficacy measures where the objective is to assess overall mean change during 3 month double-blind treatment phase, the endpoint for each LY2951742 dose arm compared with placebo will be estimated as the treatment main effect from the MMRM analysis assessing the average treatment effect across Months 1, 2, and 3.

In addition to the repeated measures analyses, the mean change from baseline to average monthly measures during the 3-month treatment phase or LOCF endpoint in SP III will be estimated for the continuous efficacy measures using ANCOVA models with covariates adjustment described in Section 5.5.1.1.

Binary Efficacy Measures

For the repeated binary efficacy measures such as responder indicators based on the number of migraine headache days, the visit wise binary outcomes indicating whether patients meet X% response criteria will be analyzed using a categorical, pseudo-likelihood-based repeated measures analysis. This analysis will be implemented using the GLIMMIX procedure in SAS to compare treatments and include the fixed, categorical effects of treatment, month, baseline medication overuse (yes versus no), concurrent prophylaxis (yes versus no), and treatment-bymonth interaction, as well as the continuous, fixed covariate of baseline value.

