An unstructured covariance structure will be used to model the within-patient errors (denoted by TYPE=CHOL in the RANDOM statement). The Newton-Raphson method with ridging will be used for nonlinear optimization (denoted by including NLOPTIONS TECH=NRRIDG). The Kenward-Roger approximation will be used to estimate denominator degrees of freedom. If the model does not converge, the Fisher's scoring algorithm will be utilized by the SCORING option in SAS.

If the model still fails to converge, the model will be fit using covariance matrices in the following order specified by a decreasing number of covariance parameters until convergence is met:

- Heterogeneous Toeplitz,
- Heterogeneous autoregressive,

- Toeplitz, and
- Autoregressive.

If necessary, both fitting algorithms will be used in the pre-specified order before proceeding to the next covariance structure in the sequence.

For models where the unstructured covariance matrix is not utilized, the sandwich estimator (Diggle et al. 1994) will be used to estimate the standard errors of the fixed effects parameters. The sandwich estimator is utilized by the EMPIRICAL option in SAS. When the sandwich estimator is utilized, the Kenward-Roger approximation for denominator degrees of freedom cannot be used. Instead, the denominator degrees of freedom will be partitioned into between-subject and within-subject portions by the DDFM=BETWITHIN option in SAS.

For the binary secondary efficacy measures where the objective is to assess proportion of patients with X% response during the 3-month double-blind treatment phase, the endpoint for each LY2951742 dose arm compared with placebo will be estimated as the treatment main effect from the categorical MMRM analysis assessing the average response rate across Month 1, Month 2, and Month 3.

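### 100% response key secondary: no visible fallback removes treatment-by-month, so a treatment-month without responders leaves the affected dose-placebo comparison with no finite estimate

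*SAP*

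**What the plan says.** SAP Section 4 (Table CGAI.4.1) lists as a key secondary endpoint "The proportion of patients with reduction from baseline of 100% in monthly migraine headache days during the 3-month double-blind treatment phase". Protocol 9.4.2 puts the key secondary tests under familywise error control together with the primary.

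SAP 5.5.10.3 (Binary Efficacy Measures) analyses the monthly responder indicators in GLIMMIX. The tested quantity averages over Months 1, 2 and 3: "the endpoint for each LY2951742 dose arm compared with placebo will be estimated as the treatment main effect from the categorical MMRM analysis". The fixed effects include treatment, month and medication overuse, and then "concurrent prophylaxis (yes versus no), and treatment-bymonth interaction, as well as the continuous, fixed covariate of baseline value". SAP 5.5.1.1 has already simplified this model: "Pooled country and the baseline value-by-month interaction will be excluded from the model in order to increase the likelihood of convergence". Treatment-by-month was kept.

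The fallback steps in 5.5.10.3 are, in order:

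- "If the model does not converge, the Fisher's scoring algorithm will be utilized by the SCORING option in SAS";
- if that is not enough, "the model will be fit using covariance matrices in the following order specified by a decreasing number of covariance parameters until convergence is met" (four simpler structures, running from heterogeneous Toeplitz down to plain autoregressive);
- whenever the covariance is not unstructured, "the sandwich estimator (Diggle et al. 1994) will be used to estimate the standard errors of the fixed effects parameters", with between-within degrees of freedom replacing Kenward-Roger.

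**The concern.** A 100% response in a month means no migraine or probable migraine day in that month. Inclusion criterion 5 in Protocol 5.1 requires at least 15 headache days in the baseline period, at least 8 of them with migraine features, so the outcome may be rare. With treatment-by-month in the model, each arm has its own logit in each month, and the test averages three of them per arm. If one of these cells has no responders, its logit has no finite maximum-likelihood value, and neither does the average that contains it. This is separation in the mean model. A different optimiser or a simpler covariance matrix does not address it.

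At stake is a test inside the error-controlled family. Followed as written, the plan could give no result for a dose, or a printed result that reflects where the algorithm happened to stop. Either way the analyst would have to choose a replacement method after seeing unblinded data.

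**Working it through.** The documents give no expected 100% response rate and no figure for this model, so there is no stated figure to reproduce. All response rates below are assumptions.

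**1. Does any fallback change the fixed effects?** In the visible text of 5.5.10.3, no. Elsewhere the SAP does let terms go: pooled country in the logistic regressions (5.5.1.1), and pooled country and/or baseline-by-month in the negative binomial sensitivity model (5.5.10.2). Treatment-by-month is never among them.

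**2. What one empty cell does.** Illustration, ignoring covariates and within-patient correlation: placebo 3/3/3 responders of 550 per month, and 12 responder-months of 275 per month on one dose.

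- Spread as 4/4/4: contrast = ln(4/271) − ln(3/547) = 0.99. SE = √[(1/3)(1/4 + 1/271 + 1/3 + 1/547)] = 0.443, so z = 2.23.
- Spread as 0/6/6: contrast = [L + 2 ln(6/269)]/3 − ln(3/547) = L/3 + 2.67, where L is the logit of the empty month. As L falls, the contrast falls without limit. A fit stopped at L = −27.6 shows −6.5 with a model SE of about 19,000 to 20,000.
- Sandwich SE at that point: an empty cell contributes nμ²/[nμ(1−μ)]², about 1/n, which is almost nothing. If different patients respond each month, variance = (1/9)[1/275 + 2(1/6 + 1/269) + 3(1/3 + 1/547)] = 0.150, SE 0.39 and z about −17. If the same patients respond throughout, variance = (4/9)(1/6 + 1/269) + (1/3 + 1/547) + (1/9)(1/275) = 0.411, SE 0.64 and z about −10.
- Interaction dropped: ln(12/813) − ln(9/1641) = 0.99, as for 4/4/4.

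**3. Fits with covariates and correlation.** The model was re-implemented in Python (not SAS) with the logit link, 570/285/285 patients and assumed rates of 0.6% to 3%. One dose-month was forced to have no responders.

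- One data set (placebo 2/3/4, affected dose 0/7/8, other dose 5/6/7): under independence the empty cell's logit was −9.9, −14.9, −19.9 and −24.9 at iterations 6, 11, 16 and 21. The main effect moved from −0.50 to −2.17, −3.84 and −5.50. The other dose's contrast stayed at 1.43.
- Unstructured, Toeplitz and autoregressive fits of that data set also diverged (main effect about −20 at iteration 30).
- In 111 simulated sets with exactly one empty cell, independence diverged in 111. The three correlated structures diverged in 102 to 107, or in 88 to 95 under very strong within-patient correlation. Nearly all the rest stopped at arbitrary values, with a negative median main effect although the simulated drug effect was beneficial.
- Among the Toeplitz and autoregressive fits that stopped in the first series, the median main effect was about −1.6 with a median sandwich SE of about 0.57, a ratio near −2.8.
- The other direction: placebo 0/4/4 of 513 and drug 3/3/3 of 257, fitted by GEE with exchangeable correlation (not one of the SAP's structures), gave an estimate of about 10, sandwich SE about 0.50 and z about 21.
- With treatment-by-month removed from the first data set, all four structures converged: log odds ratio 1.18 to 1.24, model SE 0.43 to 0.49.

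**4. How often.** SAP 5.2 plans 570/285/285 with 15% discontinuation: 0.85 × 570 ≈ 484 and 0.85 × 285 ≈ 242 evaluable. Treating months as independent, P(empty cell in one dose-placebo comparison) = 1 − [1 − (1−p₀)^484]³ × [1 − (1−p₁)^242]³.

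| Assumed monthly rate, placebo/active | (1−p₀)^484 | (1−p₁)^242 | P |
|---|---|---|---|
| 0.2% / 0.5% | 0.379 | 0.297 | 92% |
| 0.5% / 1% | 0.0884 | 0.0878 | 43% |
| 1% / 1% | 0.0077 | 0.0878 | 26% |
| 1% / 2% | 0.0077 | 0.0075 | 4.5% |
| 2% / 4% | 0.00006 | 0.00005 | 0.03% |

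Independence between months matters little. For any of the nine cells being empty (one common rate, 10% missing per month), the probability is 89%, 39%, 12% and 3% at rates of 0.5%, 1%, 1.5% and 2%. With latent within-patient correlation of 0.5 to 0.8 it is 83–87%, 35–38%, 12% and about 3%.

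**The case against.** The strongest reply is that empty cells may never occur. The plan states no rate, and at about 2% placebo and 4% active the risk is negligible. The outcome is also easier to reach than 15 baseline headache days suggests: non-migraine headache days do not count against it, and under SAP 5.4.1 a month with just over half its diary days completed is scaled up, so 16 migraine-free diary days out of 30 suffice. This stands. The risk is conditional on a rate that the sponsor may know and the reader does not.

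Second, the plan names other methods. SAP 5.5.1 mentions stratified CMH tests for postbaseline measures when needed, and Protocol 9.2 mentions Fisher's exact test where appropriate. The SAP text concerns variables without repeated measures, and neither is designated as the fallback for this endpoint, so the choice would still be made after the failure.

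Third, a small sandwich SE beside a runaway estimate is not certain. In the diverging correlated fits of the first data set the sandwich SE was itself enormous. False significance is therefore a possible outcome, not the guaranteed one. The fits were not run in SAS.

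A reader might also infer more than the documents support:

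- That the main effect is inestimable in the technical sense. It is not: the design matrix has full rank (12 of 12 columns), so the software need not flag the contrast. What is missing is a finite estimate.
- That one empty cell loses the whole endpoint. An empty dose month leaves the other dose's comparison intact.
- That a failure here stops alpha passing to other tests. The multiple-testing section (5.5.10.4) is not in the supplied text, so the endpoint's position cannot be judged, nor whether that section holds a handling rule.

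**Conclusion.** The gap is real but conditional. In the visible text, nothing in the fallback sequence for the 100% response test can repair a treatment-month without responders, and the sequence requires a standard error that can make the resulting arbitrary estimate look precise. Missing detail alone would be a smaller matter; here the written steps can lead to a wrong answer in an error-controlled test.

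The size depends on the monthly rate: a material risk per comparison at about 1% or less, about 4.5% at 1%/2%, and negligible from about 2%/4%. The conclusion assumes the logit link and the planned sample size with 15% discontinuation. It has no practical bearing on the 50% response endpoint, where empty cells are implausible. A rule fixed in advance is worth having; if the sponsor expects rates well above 2%, it will simply not be triggered.

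**What to change.** Before the study team is first unblinded at Interim Analysis #2, add a last fallback to SAP 5.5.10.3 for the 100% response endpoint:

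1. If any treatment-month cell has no responders, or if no listed covariance structure converges, refit without treatment-by-month and test the common treatment effect over Months 1 to 3. Disregard any result printed by the model with the interaction, even if the software reports convergence.
2. If a whole arm has no responders, use an exact test stratified by baseline medication overuse and concurrent prophylaxis use. Define its patient-level outcome in advance, for example 100% response in at least one of Months 1 to 3.
3. State the link function.

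The trigger uses responder counts by arm, so it should be written as a mechanical rule with no discretion.

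The cost is a few lines of SAP text and one extra program. In the fallback case the effect is assumed common across months, so the estimate is a common odds ratio rather than an average of monthly effects, and the report should say so. Step 2, if used, tests a different patient-level quantity, which should also be stated.

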- Number of migraine headache days with anti-nausea medication use is calculated as the number of migraine headache days with anti-nausea medication use during a 30-day period.
- Number of days with multiple class medication use is calculated as the number of
 days with multiple class medication use during a 30-day period.
 Multiple class medication use is defined as using at least 2 of the 5 classes (defined
 above) on a day.
- Number of migraine headache days with multiple class medication use is calculated as the number of migraine headache days with multiple class medication use during a 30-day period.
- Number of weekly migraine headache days in Month 1 is calculated as the number of migraine headache days in a 7-day period on which a migraine headache occurs. At month 1, the first 7 calendar days will be counted as week 1, the second 7 calendar days will be counted as week 2, the third 7 calendar days will be counted as week 3, and the rest of days will be counted as week 4.

Combination medications (such as aspirin/acetaminophen/caffeine) will be counted in each medication category that applies (such as NSAIDs/aspirin and Acetaminophen/paracetamol).

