5.5.7. Electronic Patient-Reported Outcomes Diary Compliance

Electronic patient-reported outcomes diary compliance at each 1-month period (including baseline, Month 1, Month 2, Month 3, ... to Month 12) as well as for SP III overall (Month 1 through Month 3) will be calculated. Diary compliance at each 1-month period is calculated as:

 $\frac{\text{Actual number of diary days in the period}}{\text{Expected number of diary days in the period}}*100$

Expected number of ePRO diary days is calculated as date of injection (date of visit for SP V) at the end of the interval minus date of injection (date of visit for SP V) at the beginning of the interval +1.

Treatment comparisons for ePRO diary compliance for each period will be performed separately using an ANOVA with treatment, pooled country, baseline medication overuse (yes versus no) and concurrent prophylaxis (yes versus no) in the model.

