To assess the robustness of the MMRM results to deviations from normality assumption, a sensitivity analysis for raw number of migraine headache days (total number of migraine headache days for each interval without normalization to 30-day period) will be conducted with a repeated measures negative binomial regression model fitted with SAS PROC GLIMMIX. The model will include treatment, pooled country, month, baseline medication overuse (yes versus no), concurrent prophylaxis use (yes versus no) and treatment-by-month interaction, as well as the continuous fixed covariates of baseline number of monthly migraine headache days and baseline-by-month interaction, log (number of compliant days within each month/30) as the offset in the model. In case of non-convergence, pooled country and/or baseline-by-month interaction may be excluded from the model. Directional consistency of treatment effects from this model and the primary analysis MMRM model as specified in Section 5.5.10.1 will be examined.

In addition, as another form of sensitivity analysis, residuals from the primary analysis MMRM model will be examined and outliers identified. Consistency of results before and after removing patients with outlier residuals will be examined.

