The number of weekly migraine headache days in Month 1 can be considered as ordinal data with possible values of 0, 1, 2, 3, 4, and etc. and it will be analyzed using an ordinal repeated measures model implemented using the GLIMMIX procedure in SAS. In this model, a proportional odds model with cumulative logit link will be used, and a random intercept will be applied to the observations for each patient to account for repeated measures. The model will include the fixed, categorical effects of treatment, pooled country, baseline medication overuse, concurrent prophylaxis use, week, and treatment-by-week interaction, as well as the continuous, fixed covariate of baseline number of migraine headache days, and baseline number of migraine headache days-by-week interaction. Log (number of compliant calendar days within each week/7) will be included as the offset in the model.

Time to Event Measures

For the following time to event measures, a Kaplan-Meier curve of the time to event and treatment group comparison using stratified log-rank test stratifying for pooled country, baseline medication overuse and concurrent prophylaxis use will be provided.

- Time to first 50% response in SP III for ITT population.
- Time to first loss of 50% response in SP V for patients who met 50% response criteria at their last injection interval and also entered SP V.
- Time to initiation of preventative treatment for migraine or probable migraine in SP V for patients who entered SP V and those who are not on concurrent preventive treatment group.

Distribution of Response Rate

Overall x% response rate during the double-blind treatment phase will be estimated for X=0, 5, 10, ..., 95, and 100, using GLIMMIX model as described earlier in this section. These estimated response rates will be plotted and points within each treatment arm will be connected to show a curve of response rates. No statistical comparisons will be conducted among different treatment arms.

Analysis for PGI-I

When analyzing PGI-I, baseline PGI-S score will be included as a covariate. Specifically, it will be analyzed with an MMRM analysis while the covariates include the fixed categorical effects of treatment, month, pooled country, baseline medication overuse (yes versus no), concurrent prophylaxis use (yes versus no) and treatment-by-month interaction, as well as the continuous fixed covariates of baseline PGI-S score and baseline PGI-S score-by-month interaction.

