Appendix Table 1. Description of Important Protocol Deviations

Category	Subcategory	Study-specific	Source	Methods of Identification
Informed Consent	ICF not obtained	Initial ICF date is missing or is after (Visit 1 date or Visit 1 lab date)	Programmable - Stats	For all patients, if initial ICF date is missing or after (Visit 1 date or Visit 1 lab date).
Form (ICF)	Improper ICF	ICF not signed prior to initiation of protocol procedures	Non-programmable - Monitor identified	Or determined by study team
		Age <18 or >65 years old at study entry	Non-programmable- Monitor identified	
		BMI ≥40 at baseline	Programmable - Stats	
		Do not meet criteria of at least 15 normalized headache days of which 8 must have features of migraine	Programmable - Stats	Number of normalized headache days <15, or number of normalized migraine headache days < 8
	leal along	At least one headache free day	Programmable - Stats	Number of normalized headache days > 29
Eligibility	Inclusion/ Exclusion	Baseline ePRO compliance <80%	Programmable - Stats	
		Female patients who have a positive serum pregnancy test prior to randomization visit	Programmable - Stats	For randomized female patients, if serum pregnancy test is positive any time prior to Visit 3
		Female patients who have a positive or no serum pregnancy test prior to randomization visit	Non-programmable- Monitor identified	
		Insufficient washout of prohibited migraine preventive medication for at least 30 days prior to Visit 2	Programmable - Stats	Patients must have discontinued such treatment at least 30 days prior to Visit 2.

Category	Subcategory	Study-specific	Source	Methods of Identification
		Insufficient washout of Botulinum toxin A and B at least 4 months prior to Visit 2	Non-programmable- Study team identified	Stats will create the list of patients meet this IPD criteria. Among those, the true IPDs will be manually added into non-programmable excel sheet
		With suicidal ideation (Q4 or Q5) within past month of visit 1.	Programmable - Stats	Randomized patients with answer "yes" for C-SSRS suicidal ideation Q4 or Q5 occurred within past 1 month of visit 1.
		Positive or no urine drug screen prior to randomization	Programmable - Stats	For randomized patients if prior to visit 3, a patient has a positive UDS result and a repeated UDS not done or last repeat UDS is positive or UDS never collected.

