		Taking prohibited migraine preventive medication for primary indication only for >7 consecutive days during study period II or III.	Programmable - Stats	Prior therapy should be excluded in the consideration.
	Taking prohibited migraine preventive medication for primary indication only for >7 consecutive days during IV.	Programmable - Stats		
Study Proce dures	Proce Conmeds	Taking prohibited medication for any indication for >7 consecutive days during study period II or III	Programmable - Stats	Prior therapy should be excluded in the consideration.
		Taking Botulinum toxin A and B for any indication during study period II or III	Programmable - Stats	Prior therapy should be excluded in the consideration.
		Corticosteroids, oral or injected, or opioids, barbiturates use >7 consecutive days during study period II or III	Programmable – Stats	Prior therapy should be excluded in the consideration.
		Start, stopping or switching dose of topirmate or propranolol during double blind phase.	Non-programmable - Monitor identified	

Category	Subcategory	Study-specific	Source	Methods of Identification
Study Proce	Visit schedule criteria	Dosing interval outside specified limits in double-blind treatment phase	Programmable – Stats	For randomized patients, compare dosing interval to allowable visit intervals between doses. Allowable dosing intervals: 21 to 37 days
dures		Dosing interval outside specified limits in open-label treatment phase	Programmable – Stats	For randomized patients, compare dosing interval to allowable visit intervals between doses. Allowable dosing intervals: 21 to 37 days
Investigat ional Product	Patient took medication not fit for use	Patient received drug that was declared "Not Fit for Use"	Non-programmable - Monitor identified	
	Dosing Error	Dose was not observed for 30 minutes at randomization visit	Programmable – Stats	Answers to CRF question 'Was the subject observed at the study site for 30 minutes post dose?" was "No".
		Other Significant violations of study drug dosing	Non-programmable - Monitor identified	
	Other	IP lost or stolen	Non-programmable - Monitor identified	
	Unblinding	Unjustified un-blinding of patient treatment assignment	Non-programmable - Monitor identified	
Administr ative/ Oversight	Suspected misconduct	Suspected Fraud	Non-programmable - Monitor identified	
	Patient privacy violation	Privacy Breach	Non-programmable - Monitor identified	

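### The exposure offset in the weekly Month 1 analysis does not suit its cumulative-logit link, the response ordering is not stated, and Week 4 is not a 7-day count

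*SAP*

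**What the plan says.** SAP 5.4.1 says the weekly measure is "calculated as the number of migraine headache days in a 7-day period on which a migraine headache occurs". It gives Weeks 1 and 2 seven days each and continues: "the third 7 calendar days will be counted as week 3, and the rest of days will be counted as week 4".

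SAP 5.5.10.3 treats the count as ordinal: "a proportional odds model with cumulative logit link will be used", with a random patient intercept. Fixed effects include treatment, week, treatment-by-week and baseline-by-week. It then adds: "Log (number of compliant calendar days within each week/7) will be included as the offset in the model". It does not say whether the model is for P(Y>=k) or P(Y<=k), where Y is the weekly count.

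The SAP uses the same kind of offset once more for migraine headache days, in the negative binomial sensitivity analysis of SAP 5.5.10.2: "log (number of compliant days within each month/30) as the offset in the model".

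Two other rules bear on diary gaps. SAP 5.4.1 sets every diary-derived endpoint to missing for a month with compliance of 50% or less. SAP 5.5.7 compares completion by arm for each monthly period: "Treatment comparisons for ePRO diary compliance for each period will be performed separately using an ANOVA".

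**The concern.** An offset is a term with its coefficient fixed at 1. In a log-link count model, log(days/7) is the right exposure term, because the expected count is proportional to the days observed. In a cumulative-logit model the linear predictor is the log odds of passing a threshold, and those log odds do not move by log(days/7) when days are lost or added. A week with missed entries is therefore adjusted by the wrong amount. If one arm misses more entries, some of that difference passes into the treatment odds ratio.

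The unstated ordering matters as well. The same offset that under-corrects when higher counts are modelled pushes the wrong way when lower counts are modelled.

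The Week 4 rule is a separate matter of definition. The measure is described as a 7-day count, but its last week is usually longer.

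**Working it through.** **1. Week lengths.** Weeks 1 to 3 reproduce the stated 7 days. Week 4 is the Visit 3 to Visit 5 interval minus 21 days. Protocol Appendix 2 gives 14 ± 1 plus 16 ± 3 days, so 30 at target with a range of 26 to 34.
- Target: 30 - 21 = 9 days.
- Within visit windows: 26 - 21 = 5 to 34 - 21 = 13 days.
- Outer limit before an important deviation (SAP Section 7, "Allowable dosing intervals: 21 to 37 days"): 0 to 16 days.

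**2. What the offset supplies.** log(9/7) = +0.25; log(5/7) = -0.34.

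**3. Log link compared with cumulative logit.** Under a log link, E(Y) = n × p, so log E(Y) = log p + log n and a coefficient of 1 is exact. For the cumulative logit, take independent days and daily probability p = 0.5. The odds of at least one migraine day are 2^7 - 1 = 127 in 7 days and 2^9 - 1 = 511 in 9 days. The shift needed is ln(511/127) = 1.39, against 0.25.

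**4. Shift needed over all thresholds.** The documents give neither the daily probability nor the day-to-day correlation, so both are assumed. The probability runs from 0.27 (8/30, from the 8-day entry minimum in inclusion criterion 5) to 0.67 (20/30, assumed). A proportional odds model for P(Y>=k) was fitted to exact count distributions, with independent days or a two-state Markov chain with lag-1 correlation 0.5.

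| Comparison | Correlation | p = 0.27 | p = 0.50 | p = 0.67 | Offset |
|---|---|---|---|---|---|
| 9 v 7 days | 0 | +0.74 | +1.21 | +1.75 | +0.25 |
| 9 v 7 days | 0.5 | +0.44 | +0.72 | +1.12 | +0.25 |
| 5 v 7 days | 0 | -0.85 | -1.41 | -2.04 | -0.34 |
| 5 v 7 days | 0.5 | -0.51 | -0.85 | -1.36 | -0.34 |

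The direction is not universal. At correlation 0.9 the offset exceeds what each of thresholds 1 to 7 needs. That holds threshold by threshold. The single fitted shift must also cover counts that a shorter week cannot reach, so the fitted contrast need not reverse.

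**5. Ordering.** At 5 days, p = 0.5 and independent days, the need is -1.41. If P(Y>=k) is modelled, -1.41 + 0.34 = -1.07 is left over. If P(Y<=k) is modelled, the offset acts against the need and -1.41 - 0.34 leaves about -1.74 (unrounded inputs).

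**6. Treatment contrast.** Same model with the offset, P(Y>=k), 7-day week, days missed at random, weeks without entries dropped, no patient random effect.
- Equal completion, no true effect: log odds ratio 0.00.
- Equal completion, true effect p = 0.5 v 0.4: -0.93 with complete diaries becomes -0.86 at 90% and -0.79 at 80% (independent); -0.60 becomes -0.58 and -0.56 (correlation 0.5).
- Unequal completion, no true effect (p = 0.27 to 0.67, correlation 0 or 0.5): -0.01 to -0.10 at 90%/88%, -0.02 to -0.26 at 90%/85%, and -0.04 to -0.51 at 90%/80%, in favour of the arm with more missed entries.

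**7. With a random patient intercept.** Simulations used 570 v 285 patients, weeks of 7, 7, 7 and 9 days, an assumed patient SD of 1 on the logit scale, and treatment and week effects only, with 90 trials per setting. The null shift was -0.05 to -0.29 at 90%/85% and -0.09 to -0.58 at 90%/80%, against a standard error of 0.12 to 0.16. With an estimated coefficient on log(days/7), it was within 0.02 of zero.

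**The case against.** **Nothing in the documents suggests a completion gap between arms.** The trial is double-blind, and entry requires at least 80% diary completion at baseline. This stands. The gaps above are illustrative, and the largest figures combine a 10-point gap, the highest daily probability and independent days.

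**The plan has safeguards.** The 50% compliance rule removes the worst Month 1 diaries. The monthly comparison would also show a sizeable gap. With an assumed between-patient SD of 10 to 20 points, the standard error of the difference is SD × sqrt(1/570 + 1/285) = 0.73 to 1.45 points, so a 5-point gap is 3.4 to 6.9 standard errors. A 2-point gap (1.4 to 2.8) might pass unnoticed, but its effect is at most about -0.10 in step 6. Both points stand as limits on the harm. Neither corrects the offset for the weeks that stay in the analysis.

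**Week 4's length is absorbed.** Week and treatment-by-week are fixed effects, so the average excess falls into the week terms. A reader might infer that the longer Week 4 biases the drug-placebo comparison. The documents do not support that: Week 4 is defined alike in randomised, blinded arms, and no Week 4 against Week 1 comparison is planned. Only an across-week reading of the fitted results would be distorted.

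**The direction is not fixed.** A reader might infer that the offset always under-corrects, or that it favours active treatment. Neither follows. The first depends on the ordering and on the strength of clustering; the second depends on which arm misses more entries, which the documents do not report.

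**Conclusion.** The offset is the wrong exposure correction for this link. That conclusion is algebraic and needs no trial data. If P(Y>=k) is modelled and days are independent or moderately correlated, it under-corrects: about +0.4 to +1.7 is needed for 9 v 7 days against +0.25, and about -0.5 to -2.0 for 5 v 7 days against -0.34. Under very strong clustering it can over-correct at all thresholds. If P(Y<=k) is modelled, its direction is wrong.

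The effect on the treatment contrast is conditional. It is nil under no effect with equal completion, a modest attenuation of a true effect, and a shift towards the arm with more missed entries when completion differs. The sizes rest on assumed daily probabilities, correlations and completion rates, so they show scale and do not predict this trial's result.

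A reader might take this as a threat to the trial's efficacy or onset conclusions. It is not one. The measure was added in SAP Version 3, is absent from Table CGAI.4.1 and is analysed without multiplicity adjustment. The primary and key secondary results, and the monthly onset rule of SAP 5.5.10.1, do not use this model. The change is worth making because it is cheap, but it is optional.

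**What to change.** In SAP 5.5.10.3, replace the offset with log(compliant days/7) as a covariate with an estimated coefficient, and state which ordering of the response is modelled. In SAP 5.4.1, define Week 4 as days 22 to 28 and treat weeks with no diary entries as missing. Week 4 may still hold fewer than seven days when the visit interval is short (five for a 26-day interval), and the covariate handles this.

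The cost is one model parameter, some SAP wording and a syntax change in the same procedure. Days after day 28 are not used in this analysis. The covariate is an average correction: no single slope can reproduce exactly the fact that five observed days cannot yield six migraine days.

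A model of migraine days out of compliant days per week (events/trials, logit link, random patient intercept) is an optional alternative or sensitivity analysis. It handles exposure directly, but it changes the estimate to an odds ratio for a migraine day, and an added overdispersion term may not converge.
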